The setting for all visits will be the Institute for Exercise and Environmental Medicine. Trials will be conducted in controlled laboratory settings. During the experimental visits (sufentanil and placebo), we will record baseline cardiovascular measures. UT-Southwestern anesthesiologist [name], or a research nurse (with direct oversight from [name]) will administer sufentanil (30 microgram tablet) or placebo tablet during each experimental visit (i.e., participants will receive only one 30 microgram tablet of sufentanil). We will assess brachial blood pressure, nervous system activity via ultrasound-guided microneurography from the upper arm, beat-to-beat arterial blood pressure via photoplethysmography, cerebral perfusion via transcranial Doppler, limb blood flow via Doppler ultrasound, heart rate via electrocardiogram, respiration rate and end-tidal CO₂ via capnography from a nasal cannula, peripheral oxygen saturation via pulse oximetry, compensatory reserve via photoplethysmography, and plasma catecholamine concentrations from serial blood samples collected throughout the visit (~4 tablespoons per experimental visit). In addition, both before and after sufentanil/placebo administration, pain perception will be accessed via a cold pressor test (2-3

Form A

STU-2021-0579

minutes of a hand placed in a water/ice slurry) and via a pressure algometer assessment (pressure applied to the hand to the point of discomfort).

Data analysis will be performed as done previously in [name] laboratory in companion studies addressing the same questions but with ketamine (STU 092017-068), fentanyl (STU 092017-069), and morphine (STU 092017-070). Specifically, we will compare cardiovascular data (inclusive of nervous system activity data) between time points (baseline and post-drug/placebo administration) and conditions. We will also assess tolerance to the simulated hemorrhage challenge between sufentanil and placebo trials. All data will be analyzed while blind to condition and with proper co-variate analysis

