Personal health information (PHI) that is collected will be kept in a key-lock filing cabinet in a key-lock room only accessible to study team members within a numeric-padlocked laboratory. As described in the eIRB portal, a coded number system will be used in place of the participants name to de-identify their research information collected. A participant ID key, only accessible to study team members, will link the participants 'information with the coded number. Additionally, we follow all applicable University of Texas Southwestern IRB and Institute of Exercise and Environmental Medicine (i.e., where the research will take place) guidelines for protecting research participant privacy.

Up to 60 participants are anticipated to enroll in this study. No study has evaluated the effects of sufentanil on lower-body negative pressure (LBNP) tolerance in humans. The power and sample size estimates are based on findings from [name] laboratory showing reduced LBNP tolerance in the heat-stressed individuals. In that study heat stressed reduced LBNP tolerance by ~70% ($P<0.001$). Though we expect sufentanil to likewise reduce LBNP tolerance, we do not anticipate as large of a reduction as that observed with heat stress. The power analysis was calculated using G*Power [Ttests – Means: Difference between two dependent means (matched pairs)] using an estimated reduction in the cumulative stress index to sufentanil of 25% relative to LBNP tolerance of a normothermic subjects taking a placebo (i.e., placebo: 988 ± 402 units; sufentanil: 741 ± 300 units). These predictions resulted in an effect size of 0.68. Having a correlation of 0.5, with a study power=0.80 at an adjusted alpha=0.05, yielded an estimated subject size of 15 individuals. That value was inflated to 30 subjects (15 male and 15 female) to permit a comparison in the primary responses within sexes. Given the potential for subject dropouts, we propose to recruit up to 60 individuals to obtain complete datasets from 30 subjects. Since the effects of sufentanil on LBNP tolerance has never been assessed, the indicated values are estimates and thus interim power analyses will be performed, with the number of required subjects adjusted based upon the variance of the obtained data.

4.b. List of the study intervention(s) being tested or evaluated under this protocol

	N/A - this study does not test or evaluate an intervention. Skip to item 4.d.		

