	Brachial blood pressure	0	several throughout visits, several in the 24-hour period after experimental visits	
	Finger blood pressure	0	continuous throughout visits	
	Microneurography for nervous system activity assessment	0	continuous throughout visits (needles placed at beginning of visits and removed before discharge)	
	Brain blood flow	0	continuous throughout visits	
	Limb blood flow	0	several throughout the experimental visits	
	End-tidal carbon dioxide	0	continuous throughout visits	
	Pulse oximetry	0	continuous throughout visits	
	Tissue oxygen saturation	0	continuous throughout visits	
	Urine sample	0	once each visit	
5	Sufentanil Administration	0	Once	

5. Safety Precautions. (Describe safeguards to address the serious risks listed above.)

- a. Describe the procedures for protecting against or minimizing any potential risks for each of the more than minimal risk research procedures listed above.

Sufentanil administration: 30 micrograms of sufentanil will be administered once during one of the two experimental visits. The product that will be used will be a Dsuvia™ sublingual tablet, or similarly packaged placebo.

Risks and their mitigation: After sufentanil administration, it is possible participants will temporarily (e.g., to several minutes) experience low blood pressure, high heart rate, disorientation, become tired or dizzy, and/or develop a headache. While some individuals may feel discomfort from one or more of these sensations, it is expected that they will subside within a few minutes. In rare cases subjects may become nauseous or vomit. In extremely rare conditions individuals may have difficulty breathing. In such extreme cases, when medical treatment is needed, we will immediately stop testing and monitor the participant until all vital signs are within safe limits. Naloxone will completely reverse all opioid effects within 2 minutes of IV administration and 5 minutes of intramuscular administration. However, at the dose in the study proposed, we do not expect that significant respiratory depression will occur. We will monitor the patient's vital signs continuously. We will monitor pulse oximetry and end tidal carbon dioxide continuously. These two monitors will provide sufficient accuracy and robustness to administer this medication safely. An anesthesiologist will be present whenever sufentanil is administered to observe and intervene should the patient exhibit the slightest evidence of respiratory depression well before any

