STU-2021-0579

patient danger should arise. Standard airway intervention equipment will always be readily available. We have safely performed similar trials, using identical experimental procedures, with ketamine (STU 092017-068), fentanyl (STU 092017-069), and morphine (STU 092017-070) administrations without major complications in 40+ young adults in the previous two years.

Upon the conclusion of the protocol, subjects will not be permitted to leave the laboratory until all of the following discharge variables are met:

- The subject presents with an Aldrete score (post-anesthesia discharge scoring system) matching baseline,
- The subject demonstrates a awareness of time, person, and place and is able to answer questions appropriately
- The subject is able to stand up and walk for 5 minutes without assistance (supervised)
- The subject is able to drink water and eat crackers without reports of nausea
- The subject able to void

To be consistent with THR/UTSW hospital guidelines—the subject will be required to have a responsible adult bring them home. The responsible adult can either drive the subject home or accompany the subject home using ground transportation (bus, train, uber, or taxi service). The subject will also receive the recommendation to have someone observe them for the rest of the day and overnight.

Lower-body negative pressure (LBNP): LBNP to pre-syncope will be used to simulate a hemorrhagic injury. LBNP is performed by the subject lying on a table with their lower body (from iliac crest) inside an airtight container. A vacuum source is connected to that container. 40 mmHg negative pressure will initially be applied to the chamber for 3 min, with this pressure decreasing by 10 mmHg every 3 min until signs and/or symptoms of pre-syncope are observed (e.g., bradycardia, sustained systolic blood pressure <80 mmHg, nausea, lightheadedness, and/or diaphoresis). This approach is a validated method to simulate a hemorrhagic challenge (see PMID: 15016789). [name] laboratory has performed this procedure on hundreds of individuals (inclusive of 40+ individuals who received ketamine, morphine, or fentanyl) without any adverse incidents.

Risks and their mitigation: The possible risks of this procedure are light-headedness, feeling faint, nausea and rarely a subject may faint. If this occurs, the procedure will be stopped and the subject will begin to feel better almost immediately.

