When the participant is undergoing any testing, they will be supervised by an ACLS trained nurse and/or physician. Of note, a board-certified anesthesiologist will always be present when sufentanil is administered. There is a fully stocked “crash cart” with a defibrillator and medications (including naloxone) within 50 feet of the laboratory. IV anti-arrhythmic medications are rapidly available if a sustained but not life-threatening arrhythmia were to occur. Airway management equipment is also stocked in that cart. Furthermore, the Texas Health Resource Emergency Room is minutes away if an escalation of care is required.

Upon screening, participants will be given contact information for a nurse to contact in case any adverse event occurs following discharge from experimental days. However, this is unlikely to occur given the short-acting effects of sufentanil and the fact that participants are not discharged until vital signs are similar to that of baseline values.

c. Will the safeguards be different between/among groups?

Yes

No

Statistical Analysis

Data was assessed for normality and are presented as means \pm SD or medians [interquartile ranges], when appropriate. Based on our prior data investigating pharmacologic agents' effects on tolerance to LBNP (12, 24, 25), a sample size of $n = 15$ was estimated, but to maintain consistency with the previous studies, we recruited 29 individuals. Paired t-tests or Wilcoxon Signed-Rank tests were used for all paired comparisons (e.g., Urine-specific gravity, CSI, pain ratings, differences in CSI between the sexes etc.). Plasma catecholamine concentrations were compared between trials (placebo vs. sufentanil) using mixed-effects model analyses. Cardiovascular and cerebrovascular responses were evaluated every 30 seconds for the cold pressor test [time x trial], and the last minute of each LBNP stage [LBNP stage x trial], with the variables with each challenge compared using repeated-measures two-way ANOVAs or mixed-effects model. If a significant interaction was identified, a post hoc Šidák multiple comparison test was employed. A < 0.05 was considered statistically significant. Data were analyzed using GraphPad Prism 9 (GraphPad Software Inc., La Jolla, CA, USA).

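### Does the LBNP stage-by-trial comparison need a rule for stages lost at pre-syncope?

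*Combined protocol and SAP*

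**What the plan says.** Item 5.a (Lower-body negative pressure) starts the chamber at 40 mmHg for 3 minutes, "with this pressure decreasing by 10 mmHg every 3 min until signs and/or symptoms of pre-syncope are observed". The example signs are "bradycardia, sustained systolic blood pressure <80 mmHg, nausea, lightheadedness, and/or diaphoresis". No last stage is fixed, so tolerance sets the number of stages in each test.

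Item 4.a plans for an "estimated reduction in the cumulative stress index to sufentanil of 25" percent ("placebo: 988 ± 402 units; sufentanil: 741 ± 300 units") with a correlation of 0.5. The Statistical Analysis section reports 29 recruited. It tests CSI by a paired t-test or Wilcoxon signed-rank test, and evaluates the physiological responses over "the last minute of each LBNP stage [LBNP stage x trial], with the variables with each challenge compared using" "repeated-measures two-way ANOVAs or mixed-effects model", with Šidák post hoc tests after a significant interaction.

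The measured responses include "beat-to-beat arterial blood pressure via photoplethysmography, cerebral perfusion via transcranial Doppler". The item 4.d table lists ECG, finger blood pressure and brain blood flow as "continuous throughout visits".

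**The concern.** Stage data are lost because of tolerance, which is the study outcome, and the plan expects sufentanil to reduce it. The loss is therefore selective and probably unequal between trials. Two of the stopping signs, bradycardia and low systolic pressure, are defined on heart rate and blood pressure, which are themselves measured during the stages.

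The two named models behave differently when stages are missing. A classical repeated-measures ANOVA needs every stage in both trials for each participant, so it must drop participants or drop stages. A mixed-effects model keeps everyone, but it relies on stopping being explained by the data it has seen.

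If the ANOVA were run deep into the protocol, late-stage comparisons would rest on a few unusually tolerant participants. The same participants would also stand in for the whole group at early stages. A blunting of compensatory responses by sufentanil could then be understated.

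**Working it through.** **Inputs.** CSI 988 ± 402 (placebo) and 741 ± 300 (sufentanil) with r = 0.5, from item 4.a; the 3-minute stages from 40 mmHg in steps of 10, from item 5.a; n = 29, from Statistical Analysis.

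**The plan's own figure.** SD of the paired difference = √(402² + 300² − 2 × 0.5 × 402 × 300) = 361.9, and 247/361.9 = 0.682, which matches the stated effect size of 0.68. The stated n = 15 reproduces with a one-sided alpha of 0.05 (power 0.807); a two-sided test needs 19. Sidedness is a separate matter, but the planning values are internally usable.

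**Assumptions needed.** The documents do not define the CSI. I take it as the sum of mmHg × minutes and assume that the planning values refer to the item 5.a schedule. CSI at the end of each stage is then 120, 270, 450, 660, 900 and 1170 for 40 to 90 mmHg.

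**Completion.** The share completing a stage is P(CSI ≥ threshold). At 80 mmHg:

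- placebo: z = (988 − 900)/402 = 0.219, giving 58.7%
- sufentanil: z = (741 − 900)/300 = −0.53, giving 29.8%
- both trials (bivariate normal, r = 0.5): 24.2%, and 0.242 × 29 = 7.0

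| Stage (mmHg) | Placebo, of 29 | Sufentanil, of 29 | Both trials |
|---|---|---|---|
| 40 | 28.6 | 28.4 | 28.1 |
| 50 | 27.9 | 27.3 | 26.6 |
| 60 | 26.4 | 24.2 | 22.8 |
| 70 | 23.0 | 17.6 | 15.7 |
| 80 | 17.0 | 8.6 | 7.0 |
| 90 | 9.4 | 2.2 | 1.6 |

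At 80 mmHg, 17.0 − 7.0 = 10.0 participants complete under placebo only and 8.6 − 7.0 = 1.6 under sufentanil only. The 7 who complete both have a mean placebo CSI of about 1341, against 988 overall.

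**How firm is 7?**

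- Normal CSI, r = 0.3 to 0.7: 6.2 to 7.8. Lognormal CSI, same correlations: 4.8 to 6.3.
- Counting anyone who reaches the start of the last minute at 80 mmHg (CSI 660 + 2 × 80 = 820): 9.7.
- A true reduction of 10% instead of 25%, r = 0.5: 10.7. No reduction: 12.3 (11.3 to 13.4 for r = 0.3 to 0.7).

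**What each model does with this.** A complete-case ANOVA through 80 mmHg keeps about 7 participants; through 60 mmHg it keeps about 23.

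To gauge bias, pressure curves were simulated in which pressure falls as a participant's remaining tolerance runs out: y = 90 − k − D·exp(−remaining CSI/τ), with k = 0 to 4 for 40 to 80 mmHg, D = 15 or 25 mmHg and τ = 150 or 300. None of these constants comes from the documents. At 60 mmHg, the 80-mmHg completers showed trial differences of −0.2 to −1.2 mmHg, against −1.5 to −3.7 in everyone with that stage in both trials. A mixed model with participant and participant-by-trial effects, judged at 80 mmHg, gave about 90% to 126% of the all-participant difference. That benchmark carries the pre-syncope value forward for participants who never reached the stage.

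**The case for a change.** The best argument for a change is that the plan offers two models with no condition for choosing, while the same section names mixed-effects models alone for the catecholamines. The loss is selective and about six times more frequent under sufentanil (10.0 against 1.6 unmatched completers at 80 mmHg). The stage data also carry the mechanistic question raised in the Background: whether an analgesic suppresses the cardiovascular response. The additions would be cheap: name the mixed model, restrict formal tests to well-populated stages, and add a paired comparison of the final minute before termination from recordings already made.

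The description of the gap stands, and so do the counts under their assumptions. The case for changing the plan is weaker:

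- **Model choice.** When the stage grid is incomplete, the mixed model is the ordinary reading of the two options. The damaging case needs the analysts to pass over it and also to run an ANOVA through 80 mmHg.
- **Stage cut-off.** Any threshold is arbitrary. Two-thirds of participants would keep 40 to 60 mmHg but remove 70 mmHg from formal testing, where about 16 pairs remain and the mixed model can use them.
- **Pre-syncope comparison.** It answers a different question, at LBNP levels that differ between trials. It says little about blood pressure or heart rate, which help define the stopping point.
- **Bias.** The marked attenuation appears only for the complete-case ANOVA, under curves that build it in. The mixed model's error had no fixed direction.

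**Conclusion.** No change follows. The section omits which stages enter, when each model applies and how a part-completed stage is counted, but it already names a method that copes with missing stages. Analysts facing an incomplete grid would be expected to use it. Showing the number contributing at each stage and trial, and reading sparse late stages with caution, is a matter of reporting.

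The figure of about 7 of 29 at 80 mmHg is an expectation from planning values, not an observed count. It rests on an assumed CSI formula, the assumption that those values came from the same LBNP schedule, approximate normality, r = 0.5 and a true 25% reduction; relaxing these gives roughly 5 to 12. It describes the analysed sample only for an analysis the plan does not specify. Some residual bias in late-stage comparisons is possible under the mixed model if stopping depends on symptoms not reflected in the stage data. Its size and sign cannot be settled from the documents. The paired CSI test of tolerance uses each participant's whole test, so it is unaffected.
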